### 5.1.2 Screening

After an individual has consented to participate in the study and informed consent is signed, that individual will be given a unique Screening Number manually created by the Investigator. The subject's unique Screening Number will be documented in the Screening and Enrollment log. The eligibility of the subject will be determined based on the inclusion and exclusion criteria listed in [Section 4, Selection of Study Population](#) and evaluated during this screening procedure.

Prior to study enrollment, demographic data will be collected from the subject, including: age, sex, race, ethnicity, height and weight, prior influenza vaccination, comorbidity, and risk of complications from influenza indicated by a calculated score. The risk assessment which incorporates medical comorbidity among other baseline characteristics is a validated predictor of risk of complications from influenza in subjects  $\geq 65$  years of age ([Hak, 2004](#)) (see [Table 5.1.2-1, Prediction Rule for Estimating the Probability of Hospitalization Due to Pneumonia or Influenza and Death Due to Any Cause](#)). Using this model, a score of  $<50$  is considered low risk and a score of  $\geq 50$  is considered high risk.

Determination of pre-existing medical conditions, for the purpose of calculating the risk score, should be made by the investigator based on his or her clinical judgment. A list of

medical conditions are presented in [Appendix 1](#) as examples for the Investigator to facilitate the completion of the co-morbidity section of the risk score.

**Table 5.1.2-1: Prediction Rule for Estimating the Probability of Hospitalization Due to Pneumonia or Influenza and Death Due to Any Cause (Hak 2004)**

Characteristic	Score a
Age, years	
<70	0
70-74	14
75-79	28
80-89	42
≥90	56
Sex	
Female	0
Male	9
Outpatient visits during the previous yearb	
0	0
1-6	11
7-12	22
>13	33
Previous hospitalization due to pneumonia or influenza	
No	0
Yes	63
Comorbidityc	
Pulmonary disease	18
Heart disease	6
Renal disease or renal transplant	12
Dementia or stroke	22
Non-hematological and hematological cancer	48

---

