8.6 Subgroups

Additional subgroup analyses will be conducted for both safety and immunogenicity assessments. Immunogenicity endpoints will also be stratified by the following subgroups:

- Age at enrollment (≥ 65 -74, ≥ 75 -84, and ≥ 85 years)
- Sex
- Race
- Previous influenza vaccination in the past 5 years (yes/no)
- Comorbidity/risk (yes/no, defined as assessment score < 50 or ≥ 50 based on scale described in Section 5.1.2 of the protocol)

Safety analysis of any unsolicited AEs and of any local, any systemic, or any other solicited AEs (all AEs combined for each such category) will be performed by stratifying for the following subgroups:

- Age at enrollment (≥ 65 -74, ≥ 75 -84, and ≥ 85 years)
- Sex
- Race

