8.8 Derived and Computed Variables

Demographics

Age and Body Mass Index will be calculated according the following formulas:

Age:

Round [(Date of Visit 1 – Date of Birth + 1) / 365.25]

Body Mass Index (kg/m²):

Mass (kg) / Height² (m²)

Immunogenicity

Values below the limit of quantification (LQ = 10) recorded as “< LQ” and values lower than the limit of quantification have been set to half that limit (5).

The rate of seroconversion is defined as the percentage of subjects with either a prevaccination HI titer < 1:10 and a post vaccination HI titer \geq 1: 40 or a prevaccination HI titer \geq 1:10 and a \geq 4-fold increase in post vaccination HI titer.

Seroconversion is defined as binary variable for subjects with non-missing values pre-vaccination and post-vaccination as:

= 1, if seroconverted (defined as the percentage of subjects with either a pre-vaccination HI titer < 1:10 and a post-vaccination HI titer \geq 1:40 or a pre-vaccination HI titer \geq 1:10 and a minimum 4-fold rise in post-vaccination HI antibody titer)

= 0, otherwise

Geometric Mean Titer (GMT)

Serum HI antibody levels of all participants will be determined in triplicate (HI1, HI2 and HI3) on serum separated from the whole blood. Pre- and post-vaccination samples will be titrated in duplicate, simultaneously. The titer assigned to each sample shall be the geometric mean of three independent determinations i.e. Assigned titer=exp[(log(HI1) +log(HI2) +log(HI3))/3].

GMT will be based on the following:

- HI antibody titer for each strain: All analyses involving HI antibody titer (namely group GMT within a treatment group) will be performed on the log scale and the resultant summary statistic back-transformed to derived GMT.

The GMT will be calculated using the following formula:

$$10^{\left\{ \frac{\sum_{i=1}^n \log_{10}(t_i)}{n} \right\}}$$

where t_1, t_2, \dots, t_n are n observed immunogenicity titers. The 95% confidence intervals for GMT will be calculated as $10^{\{M-t_{0.975,n-1}SE\}}$, $10^{\{M+t_{0.975,n-1}SE\}}$; where M and SE are the means and standard error of logarithm base 10 -transformed titers, respectively.

Geometric Mean Ratio (GMR)

GMRs measure the changes in immunogenicity titers *within* subjects.

The GMR will be calculated using the following formula:

$$10^{\left\{ \frac{\sum_{i=1}^n \log_{10}\left(\frac{t_{ij}}{t_{ik}}\right)}{n} \right\}} = 10^{\left\{ \frac{\sum_{i=1}^n (\log_{10}(t_{ij}) - \log_{10}(t_{ik}))}{n} \right\}}$$

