9. STUDY SUBJECTS

9.1 Disposition of Subjects and Withdrawals

The number of subjects screened, enrolled into the study, in each study analysis set, who completed the study, and the reasons for any premature discontinuation from the study will be presented in summary tables by treatment group, by age cohort (≥ 65 -74, ≥ 75 -84, and ≥ 85 years) and overall.

The number of subjects who are excluded from each of the FAS Immunogenicity and PPS will be summarized by treatment group, by age cohort (≥ 65 -74, ≥ 75 -84, and ≥ 85 years) and overall.

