11.1.4 Statistical Methods

All statistical analyses for HI titers will be performed on the logarithmically transformed (base 10) values. Individual HI titers below the detection limit (<10) will be set to half of that limit (5).

Co-primary immunogenicity endpoints of GMT and SCR for each virus strain contained in the vaccine will be assessed for subjects ≥ 65 years overall. For A/H1N1 and A/H3N2 strains the two aTIV treatment groups will be pooled.

Primary analysis will be performed for subjects ≥ 65 years using the PPS. The difference in SCRs will be presented with exact 95% (CIs). Miettinen and Nurminen method may be used if convergence issues (Miettinen OS, Nurminen M., 1985). Each of the four strains will be analyzed separately.

To determine the GMT ratio (adjusted analysis) a general linear model (GLM) will be fitted on log transformed (base ten) post-vaccination HI titer as the outcome variable and terms for covariates: vaccine treatment, pre-vaccination HI titer, age stratum, sex, vaccination history, age-by-vaccine interaction and study site. Potential covariate interaction effects will also be examined in the fit of the GLM. From the model, an adjusted difference in least square means (on the log scale) will be produced with 95% confidence limits. The estimated difference and the confidence limits will be back-transformed to obtain an *adjusted GMT ratio* with 95% confidence limits. Each of the four strains will be analyzed separately. The adjusted GMT ratio will be the result for which the non-inferiority assessment of the HI GMT co-primary endpoint will be based on.

The statistical models might be reduced in case they fail to converge.

The complete set of covariates that may be used in the model to calculate the adjusted GMT ratio will include treatment group (3 treatments), age sub-group (3 categories, $\geq 65-74$, $\geq 75-84$, and ≥ 85 years), sex (male or female), influenza vaccination received prior year (Y or N), pre vaccination mean GMT titer (value) and investigator site (site identifier)

The GLM specification (for each strain) is:

- *Adjusted Analysis GMT Model:* Log10-transformed Post-vaccination HI Titer = Vaccine + Age Strata + Gender + Vaccination History [y/n] + Log10-transformed Pre-vaccination HI Titer + Site + Age Strata*Vaccine.

For any strain, the interaction term *Age Strata*Vaccine* will be removed from the fit of the model if it is assessed to be not significant at the 0.05 level.

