SCRs will be analyzed using a logistic regression model, and GMT titers will be log transformed (base 10) and analyzed with a general linear model. Pre-vaccination titers will be log transformed (base 10) and entered as a continuous covariate. Vaccination history will be a categorical variable indicating whether or not an individual received an influenza vaccination in the previous year. If the proportion vaccinated in the previous year is close to 100% then this covariate may be omitted to avoid creating an unstable model. Age will be entered according to the predefined strata ($\geq 65-74$, $\geq 75-84$, and ≥ 85 years). For the logistic regressions, the odds ratios will be presented with 95% CIs for each effect in the model. For the GLM least square mean estimates for the GMT ratio will be presented with 95% confidence limits for each effect in the model.

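### The SAP rounds age to the nearest year; if that age sets the age strata, about half of 74- and 84-year-olds are placed one stratum too high

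*SAP*

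**What the plan says.** SAP 8.8 (Derived and Computed Variables) introduces the derivation under its demographics heading with "Age and Body Mass Index will be calculated according the following formulas" and then gives "Round [(Date of Visit 1 – Date of Birth + 1) / 365.25" as the rule for age. It is the only age formula in either document, and it states no decimal place or unit for the rounding.

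The strata appear in SAP 8.6 as "Age at enrollment (≥ 65 -74, ≥ 75 -84, and ≥ 85 years" and are used in several places:

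- immunogenicity and safety subgroups (SAP 8.6);
- disposition and exclusion tables, where the number of subjects "excluded from each of the FAS Immunogenicity and PPS will be summarized by treatment group, by age cohort" (SAP 9.1);
- the primary adjusted GMT model, whose terms include "pre-vaccination HI titer, age stratum, sex, vaccination history, age-by-vaccine interaction and study site" (SAP 11.1.4);
- the exploratory models, where "Age will be entered according to the predefined strata" (SAP 11.3).

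Protocol 5.1.2 provides a second possible source of age: before enrolment, "demographic data will be collected from the subject, including: age, sex, race, ethnicity, height and weight". Neither document links the SAP 8.8 age or the screening age to the strata.

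**The concern.** Rounding to the nearest year turns 74.6 into 75 and 84.6 into 85. A band written as 65-74 is ordinarily understood to hold everyone who has not reached a 75th birthday. Under the SAP formula the working cut-points become about 74.5 and 84.5 years, while the tables still carry the labels 65-74, 75-84 and 85 and over.

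What is at stake is mainly the accuracy of the age-group tables. The group aged 85 and over matters most, because it is probably the smallest and the misplaced 84-year-olds then form a larger part of it. Since the strata variable is not named, two programmers could also follow the SAP correctly and produce different subgroup tables. Age stratum enters the adjusted GMT model too, but that model serves only the 4 GMT ratios among the 16 co-primary endpoints. Eligibility is judged at screening and is not touched.

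**Working it through.** The plan gives no figure for misclassification, so there is nothing of its own to reproduce.

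**Inputs**

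- Formula: SAP 8.8, with rounding read as nearest integer.
- Strata: SAP 8.6, read in completed years.
- Sample size: 1778 enrolled, 1600 evaluable (Protocol 8.5).
- Visit 1 dates: 15 September, 1 October, 1 November and 15 December 2017 (assumed, within the 2017-2018 season).
- Age distribution: not in the documents, so assumed in step 3.

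**1. One subject.** Born 1 March 1943, Visit 1 on 15 October 2017. The difference is 27257 days, and (27257 + 1)/365.25 = 74.63, which rounds to 75. Completed age is 74. The subject moves from the 65-74 stratum to 75-84.

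**2. All birth dates.** For each Visit 1 date, every birth date giving a completed age of 65 to 94 was put through the formula.

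| Completed age | Birth dates | Placed one stratum too high |
|---|---|---|
| 74 | 365 | 183 (50.1%) |
| 84 | 365 | 183 (50.1%) |
| Any other age, 65-94 | – | 0 |

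The counts are the same for all four dates, and no subject moves down. Away from the boundaries the stratum is right, but the derived age is still one year too high for about half of birth dates.

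**3. Share of the trial.** Assume the number enrolled falls by a constant ratio r per year of age from 65, with r from 0.86 to 0.94. With no upper age limit, P74 = (1 − r)r⁹ and P84 = (1 − r)r¹⁹. The misplaced share is (183/365)(P74 + P84).

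- r = 0.86: 0.5014 × (0.0360 + 0.0080) = 2.21%.
- r = 0.94: 0.5014 × (0.0344 + 0.0185) = 2.65%.
- The largest value between these two ratios is 2.72%.
- With ages cut at 100, the range is 2.22% to 2.97%. At r = 0.94 this is 0.0265/(1 − 0.94³⁶) = 0.0265/0.8922.

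Overall this is 2.2-3.0%, or 39-53 of 1778 and 35-48 of 1600.

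A cruder assumption, that 3-10% of subjects are aged 74 or 84, gives 1.5-5%, or 27-89 of 1778.

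**4. Purity of the derived groups (same age model).**

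- 85 and over, really 84: at r = 0.86, 0.0040/(0.0490 + 0.0040) = 7.5%. At r = 0.94, 0.0093/(0.2901 + 0.0093) = 3.1%. With the cut at 100, the range is 4.8-8.2%.
- 75-84, really 74: at r = 0.86, 0.0181/(0.1723 + 0.0181 − 0.0040) = 9.7%. At r = 0.94, 6.7%.

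**5. Effect on the GMT ratio.** A B-strain comparison was simulated with 800 against 400 subjects, SD of ln titer 1.2 (Protocol Table 8.5-1) and no true difference. The assumed age effect was a fall of 0.02 log10 titer per year. The model held vaccine and age stratum main effects, with 4000 runs at each r.

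| r | Mean ratio, completed years | Mean ratio, rounded | 99th percentile of absolute change |
|---|---|---|---|
| 0.86 | 0.9995 | 0.9995 | 1.2% |
| 0.94 | 0.9992 | 0.9992 | 1.4% |

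The noninferiority margin is 1.5.

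**6. Whether truncation alone cures it.** Truncating instead of rounding, with the extra day kept, still misplaces 1 of 365 birth dates at age 74. Truncating without the extra day misplaces 1 of 366 at ages 65 and 85: the subject seen on that birthday.

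**The case against.** The strongest reply is that the misclassification rests on three readings the documents do not confirm: that the SAP 8.8 age sets the strata, that rounding means to the nearest whole year, and that the strata mean completed years. The formula stands under demographics, the strata are described as age at enrolment, and the protocol collects an age at screening. This is fair, and it is why the point is conditional. It does not remove the defect. If the formula is not used, the plan does not say what is. The reported baseline age is overstated by a year for about half of subjects in either case.

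The second reply is that no conclusion of the trial is at risk. The rule is the same in all arms, age is not described as a randomization factor, the SCR differences and CBER proportions carry no age covariate, and the subgroup tables have no success criterion. Comparisons between arms within a derived stratum remain valid. All of this stands.

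Third, the counts depend on an assumed age distribution. The simulation also omits baseline titer, sex, vaccination history, site and the age-by-vaccine interaction, all of which are in the SAP model. It is illustrative and does not describe the planned analysis. The 50% rate at the two boundary ages does not depend on the age distribution; it needs only birth dates spread evenly through the year.

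Finally, for the mean age in SAP 10.1, nearest-year rounding is close to unbiased for exact age, whereas completed years sit about half a year lower. For that summary the choice is one of convention. For the strata it is not.

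**Conclusion.** The point holds as a conditional one. Read plainly, the SAP 8.8 formula puts about half of subjects with completed age 74 or 84 one stratum too high, provided that age defines the strata and the strata mean completed years. Under the declared age assumption, 2.2-3.0% of subjects would be mislabelled. The consequence is inaccurate age-group tables, with the group aged 85 and over among those affected. No material bias is expected in the adjusted GMT ratio. The correction should be made before unblinding, but nothing here threatens a co-primary decision.

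**What to change.** In SAP 8.8, replace the formula with age in completed years at Visit 1, counted by birthday: the difference in calendar years, less one if the birthday has not yet occurred in the Visit 1 year. Drop the rounding, the added day and the division by 365.25. Truncating the present formula would remove nearly all of the error but leave a residue at a stratum boundary, whereas the birthday rule leaves none.

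In SAP 8.6 and 8.8, state that this variable defines the age strata wherever they are used, and that it is also the age reported in the demographic summaries.

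The cost is a one-line SAP change and a one-line programming change. The present formula already requires both dates, so no new data are needed.

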8.9 Analysis Software

All analyses will be performed using SAS Software version 9.3 or higher.

9. STUDY SUBJECTS

9.1 Disposition of Subjects and Withdrawals

The number of subjects screened, enrolled into the study, in each study analysis set, who completed the study, and the reasons for any premature discontinuation from the study will be presented in summary tables by treatment group, by age cohort (≥ 65 -74, ≥ 75 -84, and ≥ 85 years) and overall.

The number of subjects who are excluded from each of the FAS Immunogenicity and PPS will be summarized by treatment group, by age cohort (≥ 65 -74, ≥ 75 -84, and ≥ 85 years) and overall.

10. DEMOGRAPHICS AND OTHER BASELINE CHARACTERISTICS

10.1 Demography

Descriptive statistics (mean, SD, median, minimum and maximum) for age, height, weight, BMI, and comorbidity score at enrollment will be calculated overall and by vaccine groups.

Distributions of subjects by sex, ethnic origin (race, ethnicity), and previous vaccination status will be summarized overall, and by vaccine group.

Demographic data will be tabulated for the FAS Immunogenicity, PPS and the All Enrolled analysis sets.

10.2 Medical History

The numbers and percentages of subjects with medical history will be presented by Medical Dictionary for Regulatory Activities (MedDRA) system organ class (SOC) and preferred term (PT) by vaccine group and overall. Medical history data will be tabulated for the All Enrolled Set.

10.3 Concomitant Medications

Use of concomitant medication will be presented by treatment, therapeutic area, and preferred drug name.

Concomitant medications are all medications taken during the study period, including those started before but ongoing at vaccination.

If a start date for a medication is partially or fully missing, and it is unclear as to whether the medication is prior or concomitant, it will be assumed that it is concomitant.

Medications will be coded using the WHO Drug dictionary.

11. PRIMARY AND SECONDARY ENDPOINTS ANALYSIS

11.1 Analysis of Co-Primary Immunogenicity Objectives

11.1.1 Co-PRIMARY ENDPOINTS

The immunogenicity of study vaccines will be assessed 21 days (i.e. on Day 22) after vaccine administration by measuring the HI antibody titers to the four virus strains included in the vaccines.

The non-inferiority of aQIV compared to aTIV-1, and to aTIV-2 will be assessed for the eight co-primary endpoints of HI geometric mean titer (GMT) and SCR for each virus strain included in the vaccines as follows:

- The GMT ratio* for the A/H1N1 strain;
- The GMT ratio for the A/H3N2 strain;
- The GMT ratio for the B strain (Yamagata lineage);
- The GMT ratio for the B strain (Victoria lineage);
- The difference between the SCR** for the A/H1N1 strain;
- The difference between the SCR for the A/H3N2 strain;
- The difference between the SCR for the B strain (Yamagata lineage);
- The difference between the SCR for the B strain (Victoria lineage).

Immunogenicity results obtained from aTIV-1 and aTIV-2 for both A/H1N1 and A/H3N2 strains will be pooled for comparison with aQIV.

**The GMT ratio is defined as the geometric mean of the post-vaccination (Day 22) HI titer for aTIV-1 (or aTIV-2) over the geometric mean of post-vaccination (Day 22) HI titer for aQIV.*

***The SCR is defined as the percentage of subjects with either a pre-vaccination HI titer < 1:10 and a post-vaccination HI titer \geq 1: 40 or a pre-vaccination HI titer \geq 1:10 and a \geq 4-fold increase in post-vaccination HI titer.*

11.1.2 Statistical Hypotheses

Noninferiority of aQIV to aTIV-1 and aTIV-2

To demonstrate that vaccination with aQIV elicits an immune response that is not inferior to that of an aTIV containing the same virus strains as the US licensed adjuvanted influenza vaccine (Fluad, aTIV-1), and an aTIV containing the alternate B strain (aTIV-2) among adults \geq 65 years of age. according to the FDA Guidance on seasonal inactivated influenza vaccines (*Guidance for Industry Clinical Data Needed to Support Licensure of Seasonal Inactivated Influenza Vaccines 2007*).

aQIV will be considered to be non-inferior to aTIV if, for each of the four strains, the following statistical criteria are met:

- The upper bound of the two-sided 95% CI for the ratio of the GMTs does not exceed 1.5. The GMT ratio will be calculated by GMT_{aTIV}/GMT_{aQIV}
- The upper bound of the two-sided 95% CI for the difference between the SCRs does not exceed 10%. The difference in SCR will be calculated by $SCR_{aTIV} - SCR_{aQIV}$

In mathematical notation, the statistical hypotheses to be tested for the primary immunogenicity analysis correspond to:

$$H_0: GMTri > 1.5, \text{ for any strain}$$

$$H_a: GMTri \leq 1.5, \text{ for all strain}$$

and

$$H_0: Di > 10, \text{ for any strain}$$

$$H_a: Di \leq 10, \text{ for all strain}$$

where $GMTri$ is any of the 4 strain-specific post immunogenicity dose GMT ratios namely,

- GMT_{aTIV-1}/GMT_{aQIV} for B/Yamagata strain
- GMT_{aTIV-2}/GMT_{aQIV} for B/Victoria strain
- Pooled $GMT_{(aTIV-1 \text{ and } aTIV-2)}/GMT_{aQIV}$ for A/H1N1 strain
- Pooled $GMT_{(aTIV-1 \text{ and } aTIV-2)}/GMT_{aQIV}$ for A/H3N2 strain

and Di is the 4 strain-specific post dose SCRs ($\pi_{aTIV-1}, \pi_{aTIV-2}, \pi_{aQIV}$) difference, namely,

- $\pi_{aTIV-1} - \pi_{aQIV}$ for B/Yamagata strain
- $\pi_{aTIV-2} - \pi_{aQIV}$ for B/Victoria strain
- Pooled $\pi_{(aTIV-1 \text{ and } aTIV-2)} - \pi_{aQIV}$ for A/H1N1 strain
- Pooled $\pi_{(aTIV-1 \text{ and } aTIV-2)} - \pi_{aQIV}$ for A/H3N2 strain

where π_v denotes the SCRs for the v th vaccine (aQIV, aTIV-1, aTIV-2).

CBER Immunogenicity Criteria

The endpoints of percent of subjects achieving SC and HI titer $\geq 1:40$ at Day 22 will be assessed against the criteria described in CBER Guidance Clinical Data Needed to Support the Licensure of Seasonal Inactivated Influenza Vaccines ([FDA, 2007](#)):

- The lower bound of the two-sided exact 95% CI for the percentage of subjects achieving SC for HI antibody should meet or exceed 30% and
- The lower bound of the two-sided exact 95% CI for the percentage of subjects achieving an HI antibody titer $\geq 1:40$ should meet or exceed 60%

Assuming that $Y_{jk} \sim B(1, \pi_k)$, $Z_{jk} \sim B(1, \tau_k)$, $j=1, \dots, n$, identical and independent Bernoulli distributed random variables with π_k representing the unknown SC proportion postvaccination

and τ_k representing the unknown SP (HI titres $\geq 1:40$) proportion postvaccination in aQIV for strain k, where k denotes the 4 strains contained in aQIV vaccines, CBER requirements for the aQIV vaccine group translate into following hypothesis

$$\begin{array}{ll} H_{0k}^{(SC)}: \pi_k \leq 0.3 & \text{vs} \\ & H_{1k}^{(SC)}: \pi_k > 0.3 \\ H_{0k}^{(SP)}: \tau_k \leq 0.6 & \text{vs} \\ & H_{1k}^{(SP)}: \tau_k > 0.6 \end{array}$$

All hypotheses related to CBER criteria will be tested on unadjusted 5% significance levels.

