**Table 6.1-2: aTIV-1 Vaccine Composition**

Names of Ingredients	Quantity per dose*	Function
Active Ingredients		
Hemagglutinin (HA) and neuraminidase (NA) antigens from the influenza virus strains recommended by WHO for the manufacture of influenza vaccine for 2017-2018 season A/ Michigan/45/2015 (H1N1) A/ Hong Kong/4801/2014 (H3N2) B/ Brisbane/60/2008 (Victoria lineage)	nominally 15mcg HA/strain	Active ingredient
Adjuvant		
Squalene	9.75mg	oil phase
Polysorbate 80	1.175mg	Surfactant
Sorbitan trioleate	1.175mg	Surfactant
Sodium citrate	0.66mg	Buffer
Citric acid	0.04mg	Buffer
Other Ingredients		
Sodium chloride	4.00mg	Isotonic aid
Potassium chloride	0.10mg	Buffer
Potassium dihydrogen phosphate	0.10mg	Buffer
Disodium phosphate dehydrate	0.67mg	Buffer
Magnesium chloride hexahydrate	0.05mg	Stabiliser
Calcium chloride dihydrate	0.06mg	Stabiliser
Water for injection	up to 0.50mL	Diluent
**		
Volume of Formulation	0.5 mL	
Appearance	Liquid, milky-white emulsion	
Vaccine Presentation	Prefilled syringe	

\* the quantities indicated in this table reflect the amount in a 0.5 mL dose.

\*\* residues of special relevance: barium sulfate, cetyltrimethylammonium bromide (CTAB), chicken proteins, such as ovalbumin, formaldehyde, kanamycin and neomycin sulfate.

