**Table 6.1-3: aTIV-2 Vaccine Composition**

Names of Ingredients	Quantity per dose*	Function
Active Ingredients Hemagglutinin (HA) and neuraminidase (NA) antigens from the influenza virus strains recommended by WHO for the manufacture of influenza vaccine for 2017-2018 season A/ Michigan/45/2015 (H1N1) A/ Hong Kong/4801/2014 (H3N2) B/ Phuket/3073/2013 (Yamagata lineage)	nominally 15mcg HA/strain	Active ingredient
Adjuvant Squalene Polysorbate 80 Sorbitan trioleate Sodium citrate Citric acid	9.75mg 1.175mg 1.175mg 0.66mg 0.04mg	oil phase Surfactant Surfactant Buffer Buffer
Other Ingredients Sodium chloride Potassium chloride Potassium dihydrogen phosphate Disodium phosphate dehydrate Magnesium chloride hexahydrate Calcium chloride dihydrate Water for injection	4.00mg 0.10mg 0.10mg 0.67mg 0.05mg 0.06mg up to 0.50mL	Isotonic aid Buffer Buffer Buffer Stabiliser Stabiliser Diluent
**		
Volume of Formulation	0.5 mL	
Appearance	Liquid, milky-white emulsion	
Vaccine Presentation	Prefilled syringe	

\* the quantities indicated in this table reflect the amount in a 0.5 mL dose

\*\* residues of special relevance: barium sulfate, cetyltrimethylammonium bromide (CTAB), chicken proteins, such as ovalbumin, formaldehyde, kanamycin and neomycin sulfate

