#### 8.4.2.2.1 Statistical Hypotheses

*Noninferiority of aQIV to aTIV-1 and aTIV-2*

To demonstrate that vaccination with aQIV elicits an immune response that is not inferior to that of an aTIV containing the same virus strains as the US licensed adjuvanted influenza vaccine (Fluad, aTIV-1), and an aTIV containing the alternate B strain (aTIV-2) among adults  $\geq 65$  years of age. according to the FDA Guidance on seasonal inactivated influenza vaccines (*Guidance for Industry Clinical Data Needed to Support Licensure of Seasonal Inactivated Influenza Vaccines 2007*).

aQIV will be considered to be noninferior to aTIV if, for each of the four strains, the following statistical criteria are met:

- The upper bound of the two-sided 95% CI for the ratio of the GMTs does not exceed 1.5. The GMT ratio will be calculated by  $GMT_{aTIV} / GMT_{aQIV}$
- The upper bound of the two-sided 95% CI for the difference between the SCRs does not exceed 10%. The difference in SCR will be calculated by  $SCR_{aTIV} - SCR_{aQIV}$

In mathematical notation, the statistical hypotheses to be tested for the primary immunogenicity analysis correspond to:

$H_0: GMTr_i > 1.5$ , for any strain

$H_a: GMTr_i \leq 1.5$ , for all strain

and

$H_0: Di > 10$ , for any strain

$H_a: Di \leq 10$ , for all strain

where  $GMTri$  is any of the 4 strain-specific post immunogenicity dose GMT ratios namely,

- $GMT_{aTIV-1}/GMT_{aQIV}$  for B/Yamagata strain
- $GMT_{aTIV-2}/GMT_{aQIV}$  for B/Victoria strain
- Pooled  $GMT_{(aTIV-1 \text{ and } aTIV-2)}/GMT_{aQIV}$  for A/H1N1 strain
- Pooled  $GMT_{(aTIV-1 \text{ and } aTIV-2)}/GMT_{aQIV}$  for A/H3N2 strain

and  $Di$  is the 4 strain-specific post dose SCRs ( $\pi_{aTIV-1}, \pi_{aTIV-2}, \pi_{aQIV}$ ) difference, namely,

- $\pi_{aTIV-1} - \pi_{aQIV}$  for B/Yamagata strain
- $\pi_{aTIV-2} - \pi_{aQIV}$  for B/Victoria strain
- Pooled  $\pi_{(aTIV-1 \text{ and } aTIV-2)} - \pi_{aQIV}$  for A/H1N1 strain
- Pooled  $\pi_{(aTIV-1 \text{ and } aTIV-2)} - \pi_{aQIV}$  for A/H3N2 strain

where  $\pi_v$  denotes the seroconversion rates for the  $v$ th vaccine (aQIV, aTIV-1, aTIV-2).

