11.2.2 Statistical Hypotheses

No statistical testing will be performed for the first secondary immunogenicity objectives.

Superiority of B-strain response (GMTs and proportions of subjects with SC):

For superiority of aQIV B strain response, the hypotheses are that immunologically aQIV is superior compared to aTIV-1 and aTIV-2 for the B strain that is not included in each TIV vaccine separately. In mathematical form, these are:

$$H_{0k}^{(GMT)}: GMTr_k \geq 1 \text{ vs } H_{1k}^{(GMT)}: GMTr_k < 1 \text{ for } k=1,2$$

and

$$H_{0k}^{(SCR)}: D_k \geq 0 \text{ vs } H_{1k}^{(SCR)}: D_k < 0 \text{ for } k=1,2$$

where $GMTr_k$ is the adjusted ratio of geometric mean titer GMT_{aTIV-k}/GMT_{aQIV} of mismatched B strain for $k=1, 2$, and D_k is the differences $\pi_{aTIV-k} - \pi_{aQIV}$ of mismatched B strain Day 22 SCR differences for $k=1,2$.

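### The primary non-inferiority hypotheses compare each B strain with the trivalent vaccine that lacks it, so the matched B-strain comparison is never formally tested and the written tests pass almost automatically

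*SAP*

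**What the plan says.** SAP 11.1.2 lists the strain-specific parameters for the primary non-inferiority hypotheses. For the GMT ratio the B-strain entries are "GMT_{aTIV-1}/GMT_{aQIV} for B/Yamagata strain" and "GMT_{aTIV-2}/GMT_{aQIV} for B/Victoria strain". The SCR differences follow the same pairing: aTIV-1 minus aQIV for Yamagata, aTIV-2 minus aQIV for Victoria. Protocol 8.4.2.2.1 has the same four lines.

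The vaccine compositions are the other way round. The only B antigen in aTIV-1 is "B/ Brisbane/60/2008 (Victoria lineage" (Protocol Table 6.1-2). The only B antigen in aTIV-2 is "B/ Phuket/3073/2013 (Yamagata lineage" (Protocol Table 6.1-3).

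The secondary superiority hypothesis in SAP 11.2.2 is that "aQIV is superior compared to aTIV-1 and aTIV-2 for the B strain that is not included in each TIV vaccine separately". Its parameters are aTIV-k against aQIV for the mismatched B strain, k = 1, 2.

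The endpoint and success-criteria sections (Protocol 8.1.1.1 and 8.2.1.1; SAP 2.1.2, 2.4.1.1 and 11.1.1) refer to either aTIV or to each of the four strains. They do not say which aTIV serves as comparator for which B strain. The hypothesis sections are the only place where the non-inferiority comparator for each B strain is named.

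**The concern.** The study aims to show that adding a second B strain does not impair the response to strains already in a trivalent vaccine (Protocol 1.2, SAP 1). For a B strain, only a comparison with the aTIV that contains it answers that question. Against an aTIV without the strain, aQIV should do better even if interference is substantial, so non-inferiority shows nothing about interference.

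The written pairing also conflicts with the rest of the plan in two ways:

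- The power calculation (Protocol 8.5, SAP 5) assumes equal SCR and a GMT ratio of 1 for the B strains. That describes the matched comparison.
- Primary non-inferiority and secondary superiority become the same four B-strain contrasts with different thresholds. Meeting superiority would guarantee non-inferiority.

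If the SAP is programmed literally, the trial can claim non-inferiority for a B strain on which aQIV is clearly worse than the matched aTIV. If the team instead runs the matched comparison without correcting the text, the reported primary analysis departs from its prespecified hypotheses.

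**Working it through.** **Inputs from the documents** (Protocol 8.5, SAP 5): one-sided alpha 0.025; SCR margin 10 points; GMT ratio margin 1.5; B-strain SCR 40%; SD of log_e titer 1.2; 800 aQIV and 400 aTIV subjects per B-strain test.

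**Assumed, because the documents give no figure:** the response in an aTIV arm to the B strain it lacks. Ranges are shown below.

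**Formulas.** With p_c the aTIV rate and p_t the aQIV rate, the SCR pass probability is Φ[(0.10 − (p_c − p_t))/SE − 1.96], where SE = √(p_c(1−p_c)/400 + p_t(1−p_t)/800). For a true GMT ratio r (aTIV/aQIV) it is Φ[(ln 1.5 − ln r)/SE − 1.96], where SE = 1.2·√(1/400 + 1/800) = 0.0735.

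**The plan's own figures reproduce under equal response.**
- B-strain SCR, 40% in both arms: SE = 0.030, so Φ(0.10/0.030 − 1.96) = Φ(1.373) = 91.5%. The Farrington–Manning score variance gives exactly the stated 91.29%.
- A-strain SCR: 99.45%, as stated.
- B-strain GMT, ratio 1: Φ(0.4055/0.0735 − 1.96) = Φ(3.56) = 99.98%, as stated.
- Four SCR tests: 0.9945² × 0.9129² = 82.42%. All eight: 82.42% × 99.96% = 82.39%. Both as stated.

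**Same tests with the written pairing, aQIV performing as planned (SCR 40%).** The SCR test passes about 100% of the time for a mismatched SCR of 5% to 30%, and 99.91% at 35%. The GMT test passes more than 99.9999% of the time for any mismatched ratio of 0.9 or below. Power over the eight endpoints becomes about 0.9945² = 98.9%, limited only by the two A-strain SCR tests. The planned 82.39% therefore belongs to the matched comparison.

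**When aQIV is truly inferior to the matched aTIV:**

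| Matched aTIV vs aQIV | Matched test passes | Written test passes |
|---|---|---|
| SCR 40% vs 30% (at the margin) | 2.5% | about 100% if mismatched SCR is 10–20%; 99.98% at 25% |
| SCR 40% vs 25% | 0.01% | at least 99.99% if mismatched SCR is 5–20%; 96.5% at 25% |
| GMT ratio 1.8 | less than 0.001% | at least 99.98% if mismatched ratio is 1.0 or below |

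Second row, matched: SE = √(0.40·0.60/400 + 0.25·0.75/800) = 0.0289, so Φ[(0.10 − 0.15)/0.0289 − 1.96] = Φ(−3.69) = 0.01%. Written, mismatched SCR 20%: SE = 0.0252, so Φ[(0.10 + 0.05)/0.0252 − 1.96] = Φ(4.00), above 99.99%.

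Third row, matched: Φ[(0.4055 − 0.5878)/0.0735 − 1.96] = Φ(−4.44), below 0.001%.

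**The case against.** **The CBER criteria are a second barrier.** Study success also requires, for every strain, that the lower 95% confidence bound in aQIV reach 30% for seroconversion and 60% for titer ≥1:40. At a true aQIV SCR of 25% with n = 800 and an exact interval (at least 267 seroconverters needed), the seroconversion criterion passes with probability about 7×10⁻⁸. At 30% it passes 2.1% of the time. A 1.8-fold GMT loss from the plan's 64.6% with titer ≥1:40, assuming log-normal titers with SD 1.2, leaves about 45%, which fails the 60% criterion almost surely. On the plan's own B-strain figures, CBER would therefore block study success. This stands, but it does not prevent a false non-inferiority statement, and the protection depends on low B responses. With the matched aTIV at 50% and aQIV at 35%, a 15-point deficit, the CBER seroconversion criterion passes that strain 84% of the time. The written test then passes at least 99.95% of the time for a mismatched SCR up to 30%, and the matched test 0.01%. Likewise, if 80% of the matched arm reached 1:40, a 1.8-fold loss would still pass the 60% criterion about 57% of the time.

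**The intended reading can be recovered.** The aim, the equal-response power assumptions and the separate superiority objective all point to the matched contrast, so swapped labels are the likely cause. That is fair, but no section states the matched pairing, and SAP 14 (changes from the protocol) does not correct it.

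**Near-automatic passing is conditional.** If the mismatched aTIV responded as well as aQIV, the SCR test at 40% in both arms would pass about 91% of the time. Even then it would not test interference.

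**Conclusion.** The concern holds. In both documents, and for both GMT and SCR, the written hypotheses assign each B strain the wrong comparator. Four of the eight non-inferiority co-primaries do not address the question they exist to answer, and the matched comparison is not prespecified anywhere. The pairing follows directly from the text and needs no assumption.

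The size of the effect does rest on an assumption about the mismatched arm. Under an assumed SCR of 5% to 20%, or a GMT at or below that of aQIV, a deficit well outside the margin passes at least 99.98% of the time, against 0.01% or less with the matched test. The harm shown is a false non-inferiority claim. On the plan's assumed B responses the CBER criteria would usually stop overall success; at higher responses they may not. Because these are licensure co-primaries, the text must be corrected.

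**What to change.** In Protocol 8.4.2.2.1 and SAP 11.1.2, exchange the aTIV-1 and aTIV-2 labels in the four B-strain lines. For B/Victoria, use the GMT ratio aTIV-1/aQIV and the SCR difference aTIV-1 minus aQIV. For B/Yamagata, use aTIV-2/aQIV and aTIV-2 minus aQIV. Keep the mismatched pairings only in the superiority hypotheses. Name the matched comparator for each B strain in the endpoint definitions and success criteria as well, so that no section leaves it open.

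The cost is a wording correction in both documents before unblinding. Arm sizes stay at 800 and 400, so the stated 91.29% (SCR) and 99.98% (GMT) per B strain and 82.39% over the eight endpoints then apply as written. No further subjects or data are needed.
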